### **Pregnancy Test**

A serum pregnancy test will be performed for all women of child bearing potential at the Screening Visit. The serum pregnancy test will be sent to and performed by the central laboratory. If the serum pregnancy test is positive the subject is considered a screen failure. If the serum pregnancy test is borderline, it should be repeated  $\geq 3$  days later to determine eligibility. If the repeat serum pregnancy test is:

- Positive, the subject is considered a screen failure;
- Negative, the subject can be enrolled into the trial;
- Still borderline,  $\geq 3$  days later, this will be considered documentation of continued lack of a positive result and the subject can be enrolled into the trial.

In Period 1, a urine pregnancy test will be performed for all women of childbearing potential at the Baseline Visit prior to the first dose of study drug and at all subsequent visits. More frequent pregnancy tests will be performed throughout the study if required per local/country requirements.

- If the baseline urine pregnancy test performed at the site is negative, then dosing with study drug may begin. If the baseline urine pregnancy test performed at the site is positive, dosing with study drug must be withheld and a serum pregnancy test is required. The serum pregnancy test will be sent to and performed by the central laboratory. If the serum pregnancy test is positive, study drug must be permanently discontinued. In the event a pregnancy test comes back borderline, a repeat test is required.
- If a urine pregnancy test post baseline is positive, study drug needs to be temporarily discontinued and a serum pregnancy test is required. The serum pregnancy test will be sent to and performed by the central laboratory. If the serum pregnancy test is negative, study drug may be restarted. If the serum pregnancy test is positive, study drug must be permanently discontinued.

In Period 2, for women of childbearing potential, a urine pregnancy test will be performed at all visits and monthly at home between scheduled study visits. The results of the monthly at home tests will be communicated to the site. If a urine pregnancy test is positive, the subject must stop dosing, return to the study site and have blood drawn for a serum pregnancy test that will be analyzed at the central laboratory.

In the event a urine pregnancy test may not be performed at the protocol specified visits due to study modifications related to a state of emergency or pandemic situation like COVID-19, it can be performed by subjects at a local laboratory or it is possible for the Investigator to arrange a shipment from the study site directly to the subject's home of

urine pregnancy test kits to have the urine pregnancy test done at home (see Section 5.3.1.1 - Sub-Section "Study Drug Dispensing, Dosing, and Compliance" for details). Home urine pregnancy test should be performed monthly, regardless of ability to obtain other laboratory samples.

At each visit, the study staff should review the pregnancy avoidance recommendations with each subject of childbearing potential and male subjects receiving MTX with a partner of childbearing potential, and document this discussion in the subject's source records.

If during the course of the study a woman becomes surgically sterile or post-menopausal and complete documentation as described in Section 5.2.4 is available, pregnancy testing is no longer required.

A pregnant or breastfeeding female will not be eligible for participation in this study or be allowed to continue study drug.

### **Clinical Laboratory Tests**

Samples will be obtained for the clinical laboratory tests listed in Table 2. Unscheduled clinical labs may be obtained at any time during the study if deemed appropriate per Investigator's discretion. A certified central laboratory will be utilized to process and provide results for the clinical laboratory tests. All abnormal laboratory tests that are considered clinically significant by the Investigator will be followed to a satisfactory resolution.

The central laboratory chosen for this study will provide instructions regarding the collection, processing, and shipping of these samples.

If travel restrictions or other changes in local regulations due to state of emergency or pandemic situation like COVID-19 prevent the subject from having blood drawn for laboratory testing at the study site, it is possible for the Investigator to arrange for subjects to have laboratory work done at a local lab, hospital, or other facility to ensure the safety

assessments are conducted per protocol. Local lab results should be obtained along with reference ranges and kept within the subjects' source documentation. Local lab results should be reviewed by the investigator or designee as soon as possible and documented in the eCRF.

If laboratory samples cannot be obtained, study drug administration may be continued provided labs have been obtained within the prior 3 months, the investigator has reviewed the laboratory results and confirmed and discussed with the subject that there is no safety concern for the subject to continue use of the study drug in the absence of current lab results. The subject should be scheduled for laboratory draws as soon as feasible and no later than the next scheduled visit in order to continue the study drug administration.

If laboratory results are not available within the prior 3 months/two consecutive 12-week intervals, study drug dispensation is not allowed until the required laboratory tests are completed to ensure the safety assessments are conducted per protocol.

Blood samples will be obtained for the laboratory tests at visits specified in [Appendix D](#) and [Appendix F](#). Blood draws should be performed only after all questionnaires (HAQ-DI, Patient's Assessment of Pain, etc.), clinical assessments, and vital sign determinations are obtained.

For clinic visits where samples for serum chemistry tests are collected, subjects should be fasting (a minimum 8-hour fast) whenever possible. If a subject is not able to fast when necessary, due to unforeseen circumstances, the non-fasting status will be recorded in study source documentation.

Urine samples will be obtained for urinalysis testing at visits specified in [Appendix D](#) and [Appendix F](#). The central laboratory will be responsible for performing a macroscopic urinalysis (urine dipstick) on the collected urine specimens. Specified abnormal macroscopic urinalyses defined as leukocytes, nitrite, protein, ketones, or blood greater than negative, or glucose greater than normal will be followed up with a microscopic analysis at the central laboratory.

For any laboratory test value outside the reference range that the Investigator considers to be clinically significant, the Investigator should apply the standard of care for medical evaluation and treatment per local guidelines:

- The Investigator will repeat the test to verify the out-of-range value.
- The Investigator will follow the out-of-range value to a satisfactory clinical resolution.

A laboratory test value that requires a subject to be discontinued from study drug or requires a subject to receive treatment will be recorded as an AE.

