## **Period 2 (Long-Term Extension Period [212 Weeks])**

Period 2 will begin at Week 48 Visit after all assessments have been completed. During Period 2, subjects will visit the study site at Weeks 60, 72, 84, 96, every 12 weeks through Week 240, and Week 260/PD. A  $\pm$  7-day window is permitted around scheduled study visits. Starting at Week 48, subjects who fail to show at least 20% improvement in both TJC and SJC compared to baseline at 2 consecutive visits, despite optimization of background RA therapies (see Section 5.2.3.1 for permitted background RA therapies), will be discontinued from study drug. Therefore, the earliest discontinuation would be at Week 60, after completion of all Week 60 study visit activities.

Starting with Amendment 6, subjects receiving upadacitinib 15 mg and 30 mg QD will receive open-label upadacitinib 15 mg QD. Subjects receiving MTX will receive open-label MTX.

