## **Protocol Modifications due to State of Emergency or Pandemic like COVID-19**

Study visits may be impacted by a pandemic situation (including the COVID-19 pandemic) or any state of emergency. If visits cannot be conducted onsite due to travel restrictions or other pandemic-related reasons, virtual visits, visits at alternative locations, or changes in the visit frequency and timing of study procedures, among others may be performed. Additional details are provided in the subsequent sections. Every effort should be made to ensure the safety of subjects and site staff, while maintaining the integrity of the study.

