**Appendix F. Study Activities (Period 2)**

Activity	Wk 60	Wk 72	Wk 84	Wk 96	Every 12 Weeks a	Monthly	Every 24 Weeks a	Every 48 Weeks a	Wk 192	Final (Wk 260)/ PD Visit o	30-Day F/U Visit b
Adverse event assessment	X	X	X	X	X					X	X
Concomitant therapy	X	X	X	X	X					X	X
Patient questionnaires c PtGA Pain (VAS) HAQ-DI Morning stiffness (severity and duration)	X	X	X	X	X					X	
Latent TB risk assessment form d				X d				X d			
Central lab QuantiFERON-TB Gold test d (and/or local PPD skin test)				X d				X d			
Chest x-ray e				X e				X e			
12-lead ECG f				X f				X f		X	
X-rays (bilateral hands/feet)				X					X	X g	
Vital signs and body weight h	X	X	X	X	X					X	X
Physical exam i		X		X			X i			X	
Physician Global Assessment (PhGA)	X	X	X	X	X					X	
TJC68/SJC66	X	X	X	X	X					X	
Local urine pregnancy test j	X	X	X	X	X					X	X

Activity	Wk 60	Wk 72	Wk 84	Wk 96	Every 12 Weeks a	Monthly	Every 24 Weeks a	Every 48 Weeks a	Wk 192	Final (Wk 260)/ PD Visit o	30-Day F/U Visit b
At-home urine pregnancy test j						X					
Central lab tests hsCRP k Blood chemistry l Hematology (CBC) Urinalysis m	X	X	X	X	X					X	X
ESR (local lab)	X	X	X	X	X					X	
Calculation for drug assignment based on TJC/SJC and CDAI	X n	X n	X n	X n	X n						
Dispense study drug and subject dosing diary	X	X	X	X	X						
Review and copy subject dosing diary and perform drug reconciliation	X	X	X	X	X					X	

CBC = complete blood count; ECG = electrocardiogram; ESR = erythrocyte sedimentation rate; F/U = Follow-up; HAQ-DI = Health Assessment Questionnaire – Disability Index; hsCRP = high-sensitivity C-reactive protein; PD = Premature Discontinuation; PhGA = Physician's Global Disease Activity; PPD = purified protein derivative; PtGA = Patient's Global Assessment of Disease Activity; SJC = Swollen Joint Count; TB = tuberculosis; TJC = Tender Joint Count; VAS = visual analog scale; Wk = Week

- a. Every 12, 24, or 48 weeks, from the Week 96 Visit through Week 240.

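### The pandemic rule for withholding study drug joins two lab-age limits, 3 months and 168 days, that are not the same

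*Protocol*

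**What the plan says.** Two adjacent paragraphs of protocol Section 5.3.1.1, Clinical Laboratory Tests, cover the case where pandemic restrictions prevent a draw.

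- **Continued dosing.** Without new samples, "study drug administration may be continued provided labs have been obtained within the prior 3 months", the investigator has reviewed those results, and the absence of a safety concern has been confirmed and discussed with the subject. The missed draw is to be made up "as soon as feasible and no later than the next scheduled visit in order to continue the study drug administration".
- **Dispensing.** "If laboratory results are not available within the prior 3 months/two consecutive 12-week intervals, study drug dispensation is not allowed" until the required tests are completed.

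The same section also provides that "Unscheduled clinical labs may be obtained at any time during the study if deemed appropriate".

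The timing comes from Section 5.1 and Appendix F. Period 2 visits fall at Weeks 60, 72, 84 and 96, then "every 12 weeks through Week 240, and Week 260/PD", and a plus or minus "7-day window is permitted around scheduled study visits". Central labs and dispensing share the 12-week grid; the Appendix F footnote defines its repeating columns as "Every 12, 24, or 48 weeks, from the Week 96 Visit through Week 240". During a pandemic, Section 5.1 also says that "changes in the visit frequency and timing of study procedures, among others may be performed".

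**The concern.** The dispensing sentence is where a site looks to decide whether a subject with missed labs may have more drug. It gives two lengths joined by a slash, one nearly twice the other, and does not say whether the slash offers an alternative or a restatement. Two sites could make opposite decisions for the same subject and both claim to follow the sentence. A site using the longer length could also dispense when the paragraph above does not allow dosing to continue.

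What is at stake is safety monitoring. The interruption and discontinuation rules in Table 4 (hemoglobin, neutrophils, lymphocytes, transaminases, creatinine, CPK and others) can act only on current results.

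**Working it through.** **Inputs.** The two lengths are from Section 5.3.1.1. The 12-week spacing and the 7-day window either side are from Section 5.1. Dispensing visits are from Appendix F.

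**Step 1: do the two stated lengths agree?**
- Three calendar months, counted from any start date: 89 to 92 days.
- Two 12-week intervals: 2 × 12 × 7 = 168 days.
- Difference: 168 − 92 = 76 to 168 − 89 = 79 days. They do not agree. One interval, 84 days, is the nearer match to 3 months.

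**Step 2: how old are the labs when a draw is missed?**
- One missed draw: 84 days nominally; with windows 84 − 14 = 70 to 84 + 14 = 98.
- Two consecutive missed draws: 168 days nominally; with windows 168 − 14 = 154 to 168 + 14 = 182.

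**Step 3: what does each reading decide?**

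| Situation | Lab age (days) | 3 months | 168-day age limit | Two missed draws |
|---|---|---|---|---|
| One missed, nominal | 84 | dispense | dispense | dispense |
| One missed, late in window | about 90–98 | refuse | dispense | dispense |
| Two missed, nominal or earlier | 154–168 | refuse | dispense | refuse |
| Two missed, late in window | 169–182 | refuse | refuse | refuse |

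The conflict band after one missed draw starts at 90, 92 or 93 days if 3 months is 89, 91 or 92 days.

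**Step 4: how much of the visit window is affected?** The documents give no distribution of visit days, so assume that each is uniform over its 15 permitted days and independent of the others. There are 15 × 15 = 225 pairs, and a difference of d days between the two visits' drifts occurs in 15 − |d| of them.

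- One missed draw, age 84 + d:
  - above 89 days (d ≥ 6): 9 + 8 + … + 1 = 45 of 225, or 20.0%
  - above 91 days (d ≥ 8): 7 + 6 + … + 1 = 28 of 225, or 12.4%
  - above 92 days (d ≥ 9): 6 + 5 + … + 1 = 21 of 225, or 9.3%
- Two missed draws, age 168 + d, at or below 168 days (d ≤ 0): 15 + (225 − 15)/2 = 120 of 225, or 53.3%. This conflict exists only on the age-limit reading.

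These shares are conditional on the draw or draws already having been missed. The documents give no missed-draw rate, so no overall frequency can be calculated. Pandemic timing changes may also take visits outside the windows.

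**The case against.** The strongest reply is that the second length was never meant as an age. Draws are 12-weekly, so two consecutive intervals is a natural shorthand for two missed draws in a row. On the nominal grid that matches 3 months exactly: 84 days passes and 168 days fails. This is a fair account of the likely intent, and it stands as far as it goes. But the sentence speaks of results being available within a period, not of missed draws, so the age reading remains open. Even on the benign reading the halves part company at about 90 to 98 days.

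The second reply is that dosing has its own stop. This also stands. A reader might infer from the slash that subjects may be dosed on labs 168 days old or, with a further 12-week supply, 168 + 84 = 252 days old. The documents do not support that. A site must satisfy both paragraphs, and the administration paragraph requires labs within 3 months, investigator review and a draw by the following scheduled visit. The looser reading can release drug; it does not authorise taking it.

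A reader might also attach the end of treatment to this point. If only the Week 240 draw is missed, no later dispensing visit is scheduled, and labs from Week 228 would be (260 − 228) × 7 = 224 days old at Week 260. That is a separate matter. At Week 240 those labs are nominally 84 days old and pass on every reading, so removing the slash changes nothing there. The (260 − 240) × 7 = 140 days to the last visit are the planned schedule for everyone. Reaching 224 days also requires that no site, local or home draw is feasible for 20 weeks and that the 3-month condition is not applied in between.

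**Conclusion.** The sentence is wrong as written: it presents 89 to 92 days and 168 days as one threshold. The size of the conflict depends on the reading. As an age limit, the second length permits dispensing at a second consecutive missed draw with labs 154 to 168 days old, contrary to the 3-month condition beside it, and it also conflicts at about 90 to 98 days after a single missed draw. As a count of missed draws, it leaves only the 90-to-98-day band: 9% to 20% of in-window visit pairs after a missed draw, on the uniform assumption.

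The point is minor. It needs at least one missed draw with no local draw (Section 5.3.1), home draw (Section 5.3.1.1, optional home healthcare) or unscheduled draw obtained, and the administration paragraph already favours 3 months. It concerns Period 2 only: SAP Appendix B states that all subjects were in Period 2 when the pandemic began and that the primary and Period 1 reporting was complete. No efficacy result changes.

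**What to change.** Delete the slash and the two-interval phrase, so that the administration and dispensing sentences carry the same 3-month limit, preferably stated in days (for example, 92). Add that dispensing is refused at a second consecutive missed draw. That keeps what the phrase was probably meant to convey, and it still works if pandemic rescheduling moves visits so that a day count no longer separates one missed draw from two.

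The cost is a wording change and a note to sites. With a 92-day limit, visits with labs 93 to 98 days old after a missed draw (21 of 225 pairs, about 9%, on the uniform assumption) would need an already permitted local or home draw before resupply. A short wait is tolerable for upadacitinib, since Section 6.1.7 allows up to 30 consecutive days of interruption in Period 2. For methotrexate, Section 5.5.4 calls for an investigator decision on restarting after three or more consecutive missed doses.

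The change should go no further. Raising the limit to 98 days to absorb window drift would loosen the stated 3 months. Turning the administration condition into a check made only at dispensing would also weaken it. Capping the Week 240 supply at 12 weeks could leave a subject refused at Week 252 without drug for (260 − 252) × 7 = 56 days, beyond the 30 days just mentioned.

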**Table 2. Clinical Laboratory Tests**

Hematology (Central Lab)	Clinical Chemistrya (Central Lab)	Urinalysisb (Central Lab)	Other Laboratory Tests
Hematocrit Hemoglobin RBC count WBC count Neutrophils Bands Lymphocytes Monocytes Basophils Eosinophils Platelet count	BUN Creatinine Total bilirubin INR (reflex only) c ALT AST Alkaline phosphatase CPK Sodium Potassium Chloride Bicarbonate Calcium Inorganic phosphate Uric acid Cholesterol LDL-C HDL-C Total protein Glucose Triglycerides Albumin	Specific gravity Ketones pH Protein Blood Glucose Urobilinogen Bilirubin Leukocytes Nitrites Microscopic examination, if needed	Central Lab Tests: Serum pregnancy (bHCG) test d HBs Ag e HBs Ab e HBc Ab e HBV DNA PCR (reflex only) e HCV Ab e HCV RNA reflex only e QuantiFERON-TB Gold f Rheumatoid Factor e Anti-CCP autoantibodies e hs-CRP g IgG and IgM FSH h VZV specific IgG i Beta-D-Glucan i  Local Lab Tests: Urine pregnancy test j ESR HIV (if required) k

**Table 2. Clinical Laboratory Tests (Continued)**

ALT = alanine aminotransferase; AST = aspartate aminotransferase; bHCG = beta human chorionic gonadotropin; BUN = blood urea nitrogen; CCP = cyclic citrullinated peptide; CPK = creatine phosphokinase; DNA = deoxyribonucleic acid; ESR = erythrocyte sedimentation rate; FSH = follicle stimulating hormone; HBc Ab = hepatitis B core antibody; HBs Ab = hepatitis B surface antibody; HBs Ag = hepatitis B surface antigen; HBV = hepatitis B virus; HCV Ab = hepatitis C virus antibody; HDL-C = high-density lipoprotein cholesterol; HIV = human immunodeficiency virus; hsCRP = high-sensitivity C-reactive protein; IgG = immunoglobulin G; IgM = immunoglobulin M; INR = international normalized ratio; LDL-C = low-density lipoprotein cholesterol; PCR = polymerase chain reaction; RBC = red blood cell; RNA = ribonucleic acid; TB = tuberculosis; WBC = white blood cell; VZV = varicella zoster virus

- a. Minimum 8-hour fast. If a subject is not able to fast when necessary, due to unforeseen circumstances, the non-fasting status will be recorded in study source documentation.
- b. A urine dipstick macroscopic urinalysis will be completed by the central laboratory at all required visits. A microscopic analysis will be performed in the event the dipstick results show leukocytes, nitrite, protein, ketones, or blood greater than negative or glucose greater than normal.
- c. INR will only be measured with a separate blood sample at repeat testing if ALT and/or AST > 3 × ULN.
- d. A serum pregnancy test will be performed for all women of childbearing potential at the Screening Visit and if post baseline urine pregnancy test turns positive.
- e. HBV DNA testing is required for subjects who meet specific toxicity management criteria (See ALT/AST toxicity management criteria in [Table 4](#)).
- f. If PPD not performed.
- g. Central lab hsCRP results will remain blinded to the Sponsor, Investigator, study site personnel, and subject for all visits except Screening. Results of tests such as hsCRP may be blunted in subjects taking a JAK inhibitor, thereby limiting the clinical utility of these tests in the setting of a possible safety assessment or adverse event management. Any local hsCRP or local CRP tests should not be reported to the investigator until treatment allocation is unblinded.
- h. For more details, please refer to Section [5.2.4](#) (Contraception Recommendations).
- i. At Screening for subjects in Japan only.
- j. A urine pregnancy test will be performed for all women of childbearing potential at the Baseline Visit prior to the first dose of study drug and all subsequent visits. If the baseline urine pregnancy test performed at the site is negative, then dosing with study drug may begin. If the baseline urine pregnancy test performed at the site is positive, dosing with study drug must be withheld and a serum pregnancy test is required. The serum pregnancy test will be sent to and performed by the central laboratory. If the serum pregnancy test is positive, study drug must be permanently discontinued. In the event a pregnancy test comes back borderline, a repeat test is required. If a urine pregnancy test post baseline is positive, study drug needs to be temporarily discontinued and a serum pregnancy test is required. The serum pregnancy test will be sent to and performed by the central laboratory. If the serum pregnancy test is positive, study drug must be permanently discontinued.
- k. If required by country regulatory authorities to confirm eligibility, subjects will be tested for antibodies to HIV at Screening, and it should be documented that the test has been performed. This testing is to be done at a local lab. A subject will not be eligible for study participation if test results indicate a positive HIV infection. AbbVie will not receive results from the testing and will not be made aware of any positive result.

